Patients recruited will all be current patients of U of U dermatology department. We will send out an email to all current dermatologists within the department asking for referrals to this study. If they have patients with acne scarring who are interested in participating in this study, they will refer the patients to the study by providing the PI and sub-investigator with patient's name and university ID number. There will also be a flyer about the study available in the dermatology clinics of the U of U. The patient's medical record will then be reviewed by the PI or sub-investigator in order to determine if patient meets inclusion criteria. A recruitment letter (see documents sections), will then be mailed to the potential participants signed by the PI. The letter will give a brief description of the study, and contact information for opting out or asking for more information. Letter will let possible participants know that they will be called by the PI or sub-investigator to invite them to an introductory visit during which they will be given details about the study and their eligibility will be determined by the PI. If the patients are interested in participating in the study at this visit, they will be asked to sign the consent form (see documents section).

STUDY PROCEDURES

Screening visit- this visit takes place anytime between one week to 6 months prior to initiation of treatments at week zero. Participants will be screened based on inclusion and exclusion criteria, Fitzpatrick skin type will be determined, and full details of study are explained. If participation is desired, patients will sign the consent form at this time. Prescription may be given for oral acyclovir and topical triamcinolone.

Treatment phase

Week 0:

- Baseline full face photographs taken
- Laser treatment #1 to both sides of the face (R and L sides of the face are each treated with one of the two study lasers based on randomization)
- Review post-laser standard-of-care skin care with participants (sun avoidance, sunscreen use, moisturizer use)
- Complete VAS pain assessment (see documents attached)
- Prescription given for oral acyclovir and topical triamcinolone per protocol

Week 4:

- Full face photographs taken
- Review and evaluation of any adverse events from previous session and complete assessment of adverse events form (see attached documents)

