- Laser treatment #2 to both sides of the face (R and L sides of the face are each treated with one of the two study lasers based on randomization)
- Review post-laser standard-of-care skin care with participants (sun avoidance, sunscreen use, moisturizer use)
- Complete VAS pain assessment (see documents attached)
- Prescription given for oral acyclovir and topical triamcinolone per protocol

Week 8:

- Full face photographs taken

- Review and evaluation of any adverse events from previous session and complete assessment of adverse events form (see attached documents)
- Laser treatment #3 to both sides of the face (R and L sides of the face are each treated with one of the two study lasers based on randomization)
- Review post-laser standard-of-care skin care with participants (sun avoidance, sunscreen use, moisturizer use)
- Complete VAS pain assessment (see documents attached)
- Prescription given for oral acyclovir and topical triamcinolone per protocol

Week 24:

- Full face photographs taken
- Review and evaluation of any adverse events or serious adverse events
- Complete physician assessment of improvement of acne scarring (see documents attached)
- Participants fill out final satisfaction survey (see documents attached)

STUDY TREATMENT

Both laser treatments are FDA approved for acne scarring and both are considered as part of standard of care of acne scarring. The procedures that are for research purposes only are:

- blinding the participant to which side of face receives which laser
- randomization of which side of face receives which laser
- review of clinical photos by blinded dermatologist

STATISTICAL CONSIDERATIONS

Analysis method will be based on the following table:

Outcome	When measured	Analysis Method
VAS pain score after each treatment	After each treatment	T test to compare means across laser type at each time point. Repeated measures mixed effects models to compare effects across study.
Equivalence across laser type.		One sided t test for non-inferiority or equivalence.
Proportion Satisfied or Extremely Satisfied	Final visit at 24 weeks (3 moths post final laser tx)	Verify that there is no stat. sig dif between laser types, Then using score of side with lowest satisfaction test if proportion is different from 0 or proposed placebo effect.

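### Which laser is fired first is neither randomised nor recorded, so treatment order may be confounded with laser in the VAS pain comparison

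*Combined protocol and SAP*

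**What the plan says.** Randomisation is mentioned in two places. STUDY TREATMENT lists, among the research-only procedures, "randomization of which side of face receives which laser". STUDY PROCEDURES repeats at weeks 0, 4 and 8 that "R and L sides of the face are each treated with one of the two study lasers based on randomization". Neither place says which laser or which side is treated first, or whether that is fixed, alternated, randomised or written down.

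A session is numbered as one treatment that covers the whole face: "Laser treatment #1 to both sides of the face". At each of the three visits the next bullet is the skin-care review, followed by a single pain step, "Complete VAS pain assessment (see documents attached". The VAS form is an attachment and is not shown.

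In the analysis table under STATISTICAL CONSIDERATIONS, the outcome is "VAS pain score after each treatment". The methods are "T test to compare means across laser type at each time point" and "Repeated measures mixed effects models to compare effects across study". No order or period effect is named for either.

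Pain is among the immediate side effects listed under SAFETY MONITORING. Hypothesis 2 expects a better side-effect profile for the picosecond laser. PURPOSE & OBJECTIVES labels the side-effect comparison exploratory.

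**The concern.** Two devices used on one face in one session must be used in sequence. Randomising the side balances left against right, but it balances first against second only if order happens to follow side. If order follows the device, the laser contrast and the order contrast are the same contrast.

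Pain ratings are open to order effects. The second side is treated after a painful stimulus has just been felt. If both sides are rated at the end, the first is also rated after a longer delay and across a second, different stimulus. With a habitual device order, the shift has the same sign at weeks 0, 4 and 8. Pooling the sessions would then narrow the interval around a biased value. An order effect could be reported as a difference in tolerability between the lasers, which is part of what hypothesis 2 asserts. If the order used was never recorded, it cannot be adjusted for afterwards.

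**Working it through.** **Inputs from the documents.** 18 completers and 20 enrolled (Power and Sample Size); two-sided alpha 0.05 (STATISTICAL CONSIDERATIONS); three sessions, both sides treated at each.

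**Inputs not in the documents.** The order effect d, the SD of the within-person VAS difference, and the share p of participants in whom a given laser goes first. All three are assumed below and varied.

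**The plan's own figure.** A paired non-inferiority t test with n = 18, margin 0.5, SD 0.71 and one-sided alpha 0.025 has noncentrality (0.5/0.71) × √18 = 2.99 on 17 df. Its power is 0.80388, exactly as printed, and a 10% dropout allowance gives 20. This figure concerns satisfaction, not pain. It matters here only because it shows that the plan was sized on paired data, so I take the VAS t test as paired too; the table does not say.

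**Bias.** Let the paired VAS difference be laser effect + d when laser A is first, and laser effect − d when it is second. The mean difference is then laser effect + (2p − 1)d.

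- p = 1 (one laser always first): bias = d.
- p = 12/18 = 2/3: bias = 0.333d, that is 0.083 SD for d = 0.25 SD and 0.167 SD for d = 0.5 SD.
- p = 1/2: bias = 0.

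**False-positive rate at one session.** No true laser difference, n = 18, two-sided 0.05 paired t test. For p = 1 this is exact from the noncentral t with noncentrality (d/SD) × √18; for the other rows it comes from 100,000 simulated trials.

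| Share with the same laser first | d = 0.25 SD | d = 0.5 SD |
|---|---|---|
| All (p = 1) | 0.170 | 0.516 |
| Two thirds | 0.056 | 0.070 |
| Half (balanced) | 0.044 | 0.029 |

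In the balanced row the order effect adds only variance to the paired differences, so an unadjusted test is conservative rather than biased.

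**In VAS points, p = 1, assuming a 0–10 scale.**

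| SD of paired difference | d = 0.5 points | d = 1.0 point |
|---|---|---|
| 1.5 | 0.266 | 0.760 |
| 2.0 | 0.170 | 0.516 |
| 2.5 | 0.126 | 0.360 |

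**Which habit matters.** If the operator always uses the same device first, p is 1 or 0 whatever the side allocation. If the operator always starts on, say, the right, then the laser that goes first is the one allocated to the right. Randomising side then randomises order, and p is 1/2 in expectation.

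**The case against.** The strongest reply is that the documents do not show a biased order; they are silent on it. A habit of starting on the same side is as plausible as a habit of starting with the same device, and under it side randomisation already removes the systematic bias. That stands. A reader might infer that randomising side gives no protection; that is true only if order follows the device, and nothing in the documents says it does.

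A reader might also infer that the first side is definitely scored from memory after both sides are done. The visit list points that way, because there is one pain step after a step covering both sides. But the bullets are not declared to be a timed sequence, the timing entry in the analysis table could mean after each laser, and the form that would settle it is not shown. Separate, immediate ratings may already be intended. This weakens the recall argument but not the order argument: a rating taken straight after each side can still depend on whether that side was first or second.

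Finally, the large percentages belong to the extreme case. With one laser first in two thirds of participants the inflation is slight. The comparison is also exploratory, with patient-reported adverse events as its stated endpoint, and VAS pain does not drive the sample size. All of this limits the weight of the point. It does not answer the fact that the plan leaves the protection to chance.

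**Conclusion.** The point holds as a possible, avoidable confounding. Nothing in the plan prevents firing order from tracking laser, and no order term is named. If order tracks laser completely, neither the t test nor the mixed model can separate the two.

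The size depends on unknowns: from no bias when order is balanced up to the whole order effect when one laser is always first. A reader might take the 52% as the error rate of this trial. It is not: it requires a fixed device order and an order effect of half an SD, and the documents give neither. The percentages show only why order should not be left open.

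The reach is limited to VAS pain, and so to part of hypothesis 2. The week 24 photographic and satisfaction outcomes and the sample size are unaffected. It is worth correcting before the first session because the correction is cheap and cannot be made afterwards if order is unrecorded.

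**What to change.** 1. Extend the allocation list to four sequences: picosecond laser on the right or left, crossed with picosecond laser first or second, with 5 of the 20 participants in each.
2. Keep the side fixed for all three sessions and alternate the order between sessions, so that each session is balanced 10 to 10. Record the order actually used.
3. Collect a separate VAS, labelled by side, straight after that side is finished and before the other begins. If the attached form already does this, say so in the visit schedule.
4. Add order (first or second) as a fixed effect in the planned VAS mixed model, and name that model as the main pain comparison. The per-session paired t tests can stay: once order is balanced, an additive order effect does not bias them. If both expected dropouts came from the same order group, the split would be 10 to 8 and the residual bias (2 × 10/18 − 1)d = 0.11d, which the model term would absorb.

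The cost is a new allocation list, a two-line VAS form and one model term, with no extra participants, visits or procedures. The operator loses free choice of device order. An additive order term does not remove unequal carry-over, where pain from one laser colours the rating of the other more than the reverse; that limitation should be stated when pain is reported.

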Mean of scores from 3 physician evaluators on improvement in texture and overall appearance	Week 24 photos (3 months post final treatment)	T test to compare means across laser type. Repeated measures mixed effects models to compare effects across all study timepoints.

All analyses will be conducted using SAS software version 9.4. All test will be two-sided with an alpha level of 0.05 with the exception of the non-inferiority analysis which will be a one-sided test with and alpha level of 0.025.

Power and Sample Size

Sample size estimation is based on the primary aim of patient-reported scar improvement. The goal of the study is to show non-inferiority of the two types of laser treatments. Cho (2009) found that the mean difference in patient satisfaction scores (scores ranged from 0 to 3) across the two laser treatments was -0.75 with a standard deviation of 0.71 Using this standard deviation of 0.71 to power for a non-equivalence test, it was found that a sample sizes of 8 achieves 80% power to detect non-inferiority using a one-sided t-test.

Results from PASS software:

	Non-Inferiority	Actual	Significance		Standard
Power	N	Margin	Difference	Level	Deviation
		(-NIM)	(D)	(Alpha)	Beta
					(S)
0.80388	18	-0.500	0.000	0.02500	0.19612
					0.710

If the goal is to establish non-inferiority of the new laser to the old, 18 subjects are needed. The assumption is that there is no difference in the two lasers, but the investigator is willing to accept a margin of inferiority of 0.5. Allowing for a 10% dropout rate, 20 subjects would need to be enrolled. The investigator would also like to establish that either laser type achieves a certain proportion of good or excellent results on subjective assessment. Assuming that the two methods are equivalent, we want to determine if the effect of either side would be better than a placebo effect or a much less effective treatment. The following table gives scenarios of detectable difference if 18 subjects complete the study for a two-sided test at alpha = 0.05.

With 18 subjects completing the study and a power of 0.80 the following differences between those rating either laser treatment as satisfied or very satisfied could be detected:

% satisfied/ext. satisfied if no effect (as compared to an ineffective or no treatment)	% satisfied/ext. satisfied if an effect	Detectable difference
0.0500	0.2339	0.1839
0.1000	0.3318	0.2318
0.1500	0.4126	0.2626
0.2000	0.4839	0.2839
0.2500	0.5487	0.2987
0.3000	0.6085	0.3085

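### The trial is sized on the 0-3 satisfaction score, but the analysis table compares the lasers on satisfaction only after cutting it to yes/no, and never ties the sized t test to the score

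*Combined protocol and SAP*

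**What the plan says.** Power and Sample Size states that "Sample size estimation is based on the primary aim of patient-reported scar improvement". It takes from a cited study a "mean difference in patient satisfaction scores (scores ranged from 0 to 3) across the two laser treatments was -0.75 with a standard deviation of 0.71". It uses that SD with a true difference of 0, and says that "the investigator is willing to accept a margin of inferiority of 0.5". The PASS row gives N = 18, one-sided alpha 0.025 and power 0.80388.

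The analysis table in Statistical Considerations has two rows that bear on this:

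- **The satisfaction row**, measured at the 24-week final visit. Its outcome is "Proportion Satisfied or Extremely Satisfied". Its first step is "Verify that there is no stat. sig dif between laser types", with no test named. Its second step tests the proportion on the less satisfied side against 0 or a placebo rate.
- **The equivalence row**, directly below VAS pain. It gives a one-sided t test for non-inferiority or equivalence, with no outcome and an empty time-point cell.

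No row names the 0-3 satisfaction score. The detectable-difference table that closes Power and Sample Size covers the proportion only in the one-sample comparison with an ineffective treatment. No power is given for comparing the two lasers on the proportion.

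**The concern.** The scale that justifies 18 completers is not the scale on which the table compares the lasers for satisfaction. In a split-face design each participant rates both sides. Once the ratings are cut to yes/no, only participants whose two ratings fall on opposite sides of the cut carry information. Someone extremely satisfied with one side and merely satisfied with the other counts as showing no difference, as does someone whose ratings differ only among the lower categories.

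This check decides whether the plan treats the lasers as alike and moves on to the placebo comparison. If it is run on a less sensitive scale, a real difference as large as the plan's own margin is more likely to pass unseen, although the survey already holds the finer information. Whether a non-significant result can show similarity at all is a separate question; the loss from the cut arises whichever kind of between-laser test is used.

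**Working it through.** **Inputs from Power and Sample Size.** SD of within-person differences 0.71; margin 0.5; true difference 0 for non-inferiority; one-sided alpha 0.025 (two-sided 0.05 for other tests); 18 completers. One sentence of the prose says 8, but the PASS row and the later text say 18. A sample of 8 would give 40.5% power.

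**Step 1: the plan's figure.** For a paired t test, the noncentrality is 0.5 / 0.71 × √18 = 2.988, with 17 degrees of freedom and critical value 2.110. Power = 0.80388, as stated.

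**Step 2: the same data, asked the other way.** A two-sided 0.05 paired t test at a true difference of 0.5 has the same noncentrality and critical value, so its power is also 0.804. This is a different test under a different truth from the plan's 80%. The two agree only by symmetry.

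**Step 3: the cut, with normally distributed ratings.** Assumed, because the documents do not give them: the correlation r between sides, the position of the cut, and McNemar's test as the paired test. The per-side SD is 0.71 / √(2(1 − r)). Let p be the chance that only the better side is rated satisfied, and q the chance that only the worse side is. Power comes from full enumeration of the 18-pair outcomes at two-sided 0.05.

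Example with r = 0.5: per-side SD = 0.71 / √1 = 0.71. With the cut midway between the side means, each mean lies 0.25 / 0.71 = 0.352 SD from it, so 64% and 36% are satisfied; p = 0.336, q = 0.061.

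| Correlation | p, q (central cut) | Exact McNemar | Uncorrected McNemar |
|---|---|---|---|
| 0 | 0.477, 0.096 | 49% | 59% |
| 0.25 | 0.412, 0.079 | 42% | 54% |
| 0.5 | 0.336, 0.061 | 31% | 47% |
| 0.75 | 0.238, 0.042 | 14% | 36% |

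Moving the cut 0.5 points off centre gives 10% to 45% over the same correlations.

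**Step 4: the cut, with one-step changes.** Suppose ratings differ by at most one category. The plan's figures require p + q = 0.71² + 0.5² = 0.7541 and p − q = 0.5 when every change crosses the cut, so p = 0.627 and q = 0.127. Power on the cut is 64% (exact) or 73% (mid-p or uncorrected). The paired t test on the score has 77% here. If only half of the changes cross, the cut gives 25% to 41%.

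**Step 5: is there a ceiling?** No. With rounded ratings on 0-3 and a narrow spread (latent SD 0.4, satisfied 89% against 50%), uncorrected McNemar reaches 71%. In a contrived case where all the gains but none of the losses cross the cut (p = 0.627, q = 0), it exceeds 99%.

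**The case against.** The strongest reply is that the score comparison is already in the plan. The equivalence row prescribes a one-sided t test, and the sample-size text describes the sized analysis in the same terms. The alpha statement exempts a single non-inferiority analysis at 0.025, and a t test is not the natural test for a proportion. On that reading the sized test is present and merely unlabelled. This largely stands. A reader might infer that the score-scale comparison was dropped in favour of the cut; the documents do not show that. They do leave the row without an outcome or time point, and the check inside the satisfaction row is on the cut either way.

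A second reply is that the cut has a stated purpose: showing that either laser beats a placebo-like rate. That justifies the proportion for the one-sample test, which has its own detectable-difference table. It gives no reason to compare the lasers with each other on the cut.

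Third, the satisfaction row names no test and the survey form is not shown, so every figure for the cut depends on assumptions. That is correct. A reader might infer that the cut holds power below some fixed ceiling, or always costs a large amount. Steps 4 and 5 rule out both: against the mid-p or uncorrected test the loss can be about 4 points (77% to 73%), and a contrived case reverses it.

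Finally, a reader might infer that the plan promised 80% power for the check in the satisfaction row. It did not: the 0.80388 is for non-inferiority under the premise that "The assumption is that there is no difference in the two lasers".

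**Conclusion.** The point holds as a mismatch between the sized scale and the analysed scale, together with an unlabelled test. The sample size is arithmetically sound for the 0-3 score. The table does not assign the sized test to that score, and the one between-laser check it does assign to satisfaction discards part of the rating.

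At a true difference of 0.5 points with 18 pairs, the score gives about 77-80% power. A central cut with correlation 0 to 0.5 gives about 30-60%, so such a difference would be missed in roughly 4 to 7 trials in 10 rather than about 2. Across the ordinary scenarios examined, the range on the cut is about 10% to 73%. These figures rest on the plan's SD of 0.71 and on assumed correlation, cut position, rating spread and version of McNemar's test. The direction of the loss is the usual one; its size cannot be fixed from the documents. The change is worth making because it costs almost nothing.

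**What to change.** - **Satisfaction row.** Make the between-laser comparison on the within-person difference in the full Week 24 satisfaction score: paired t test with 95% confidence interval, and Wilcoxon signed-rank as a sensitivity analysis.
- **Equivalence row.** Name that score and Week 24 as the outcome and time point of the one-sided 0.025 non-inferiority t test with margin 0.5. State how the survey categories are coded, so that it is clear what 0.5 points means on the form actually used.
- **Proportion satisfied.** Keep it for the one-sample comparison with a placebo rate, and report it for each laser as a description.

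This changes analysis-plan wording only: the same survey and visits, and no extra participants. The one drawback is that a mean score difference is slightly less direct for clinicians than a percentage satisfied, and reporting the proportion alongside it covers that.

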A recent study investigated the safety and efficacy of a 755-nm alexandrite picosecond pulse duration laser with diffractive lens array for the treatment of facial acne scarring (Brauer et al. 2015). This laser has also been FDA approved for treatment of atrophic acne scars. The evolution from nanosecond to picosecond lasers can deliver more targeted energy, and with lower fluence, leading to fewer adverse effects. An innovative optical attachment, a diffractive lens array, has been developed that augments distribution of energy to the treatment area. This method has a greater pattern density per pulse, and was shown in this study to improve appearance of acne scars.

In the Brauer study, patients received 6 treatments with a 755-nm picosecond laser with a spot size of 6 mm, fluence of 0.71 J/cm², repetition rate of 5 Hz, and pulse width of 750 picoseconds in combination with a diffractive lens array, allowing for greater surface area and pattern density per pulse. This treatment produced improvement in appearance and texture at 3 months after the last treatment, with objective findings similar to those published for a series of fractional ablative laser

treatments. The study demonstrated high patient satisfaction and no significant lasting side effects among Fitzpatrick skin types I through V.

Introduction:

We will compare these two lasers in the treatment of acne scarring by performing a split faced randomized trial with three treatments over 3 months. Photographs will be taken prior to treatment and after final follow up with photographic review by blinded reviewer.

Hypotheses for this study:

1- There is no significant difference in efficacy of acne scar treatment with fractionated 1550-nm laser and 755-nm picosecond laser in combination with a diffractive lens array.

2- The 755-nm picosecond laser in combination with a diffractive lens array has superior side effect profile as compared to fractionated 1550-nm laser in treating acne scars.

PURPOSE & OBJECTIVES

Objective: To compare efficacy and safety of fractionated 1550-nm laser and 755-nm alexandrite picosecond laser in combination with a diffractive lens array, in treatment of moderate to severe acne scars.

Primary Endpoint: Improvement in acne scarring measured by photographic review. Measured by blind reviewer and quantitative 3D imaging.

Exploratory Objective: Comparing side effects of the different lasers.

Exploratory Endpoint: measure side effects by patient reported adverse events.

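### The satisfaction row treats a non-significant difference as proof that the lasers are alike, which 18 pairs cannot show, and one one-sided t test can show non-inferiority but not equivalence

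*Combined protocol and SAP*

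**What the plan says.** The analysis table in Statistical Considerations has two relevant rows.

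- **Satisfaction row** (proportion satisfied or extremely satisfied, final visit at 24 weeks). The first step is "Verify that there is no stat. sig dif between laser types". The second takes the side with the lower satisfaction and tests its proportion against zero or a proposed placebo effect. No between-laser test, margin or single reference rate is given.
- **Equivalence row**. The method is "One sided t test for non-inferiority or equivalence". In the text as extracted, the time cell is empty and the row follows VAS pain directly.

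Below the table, difference tests are set at two-sided 0.05 and non-inferiority at one-sided 0.025. Power and Sample Size adds "The goal of the study is to show non-inferiority of the two types of laser treatments", and "the investigator is willing to accept a margin of inferiority of 0.5". The SD of 0.71 comes from a cited study that used "patient satisfaction scores (scores ranged from 0 to 3" points). The PASS row gives power 0.80388 for N = 18. The detectable-difference table, with power 0.80 and 18 completers, is introduced by "Assuming that the two methods are equivalent, we want to determine if the effect of either side would be better than a placebo effect".

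**The concern.** A significance test that fails to reject says only that the data did not exclude a zero difference. Without a margin it does not bound how large the difference may be, and in a small trial it will often fail to reject when the difference is considerable. Using it to verify likeness makes a small sample look like evidence of similarity.

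The equivalence row has a related fault. A single one-sided test bounds the difference in one direction. It can show that one laser is not worse by the margin, but it cannot exclude that this laser is better by more than the margin.

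At stake is a statement that the two lasers are alike, on satisfaction or more broadly, that the planned tests could not support. If the preliminary check is read strictly, it also blocks the comparison with placebo whenever the lasers differ significantly, although a good result on the worse side would then be just as informative.

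**Working it through.** **Inputs from the plan.** 18 completing pairs; two-sided 0.05 for difference tests; one-sided 0.025 for non-inferiority; margin 0.5; SD of the paired difference 0.71; true difference 0; ten pairs of proportions in the detectable-difference table. **Assumed, because the plan is silent:** the version of McNemar's test, true satisfaction rates of 80% and 60%, and within-person correlation ρ of 0 to 0.4.

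**1. The plan's own power.** Paired t test, 17 df, noncentrality 0.5 / (0.71/√18) = 2.988, critical value 2.110. Power = 0.80388, which matches PASS. (One sentence gives a sample size of 8. That would give 0.405, so 18 is used here.)

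**2. Smallest observed gap that can be significant.** For a given gap, p is smallest when all x discordant pairs favour one laser.

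| Test | p for an x–0 split | Not significant | First significant |
|---|---|---|---|
| Exact | 2 × 0.5^x | x = 5: 0.0625 | x = 6: 0.031 (6/18, 33 points) |
| Mid-p | 0.5^x | x = 4: 0.0625 | x = 5: 0.031 (5/18, 28 points) |
| Uncorrected chi-square | chi-square = x, 1 df | x = 3: 0.083 | x = 4: 0.0455 (4/18, 22 points) |

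Under all three, a gap of 3/18 (17 points) can never fail the check.

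**3. How often the check passes when the lasers differ.** With true rates of 80% and 60%, P(both satisfied) = 0.48 + ρ√(0.8·0.2·0.6·0.4). The discordant probabilities are 0.80 and 0.60 minus that value, so 0.32 and 0.12 at ρ = 0. Summing over all outcomes for 18 pairs:

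| P(not significant) | ρ = 0 | ρ = 0.2 | ρ = 0.4 |
|---|---|---|---|
| Exact | 0.861 | 0.851 | 0.850 |
| Mid-p | 0.785 | 0.758 | 0.731 |
| Chi-square | 0.776 | 0.723 | 0.632 |

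**4. What identical observed rates leave open.** With k discordant pairs split evenly, the 95% score interval for the paired difference has half-width z√(z² + k)/(n + z²), with z = 1.96 and n = 18. For k = 0, 2, 4, 6, 8 this gives ±0.176, 0.217, 0.251, 0.282, 0.309.

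**5. Effect on the comparison with placebo.** The lower side is tested by an exact binomial test with upper tail at most 0.025.
- Type I error without the check, with the worse side at the reference rate and the other 0 to 40 points higher: at most 0.0212.
- Power lost to the check if the lasers are equal, over the ten scenarios: at most 0.0016 (exact), 0.0056 (mid-p) or 0.0149 (chi-square).
- If the lasers differ and a significant difference stops the procedure: at an assumed 90% and 60% against a 20% reference, power falls from 94% to between 17% and 63%, depending on the test and ρ.

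**6. Power of the lower-side test itself.** The plan's 0.80 reproduces for one side by a normal approximation (0.798 to 0.800 in the rows checked). Requiring the lower of two equal sides to pass the exact test gives 0.339 (10% row, ρ = 0) to 0.638 (40% row, ρ = 0.4). Part of the fall comes from the exact test: for one side it gives 0.582 in the 10% row and 0.750 in the 50% row. If each side is tested and a win on either counts, one-directional error reaches 0.042 (35% reference, ρ = 0) against 0.025.

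**7. Equivalence.** Two one-sided tests within ±0.5, same SD, true difference 0, n = 18: power 0.609 at 0.025 per side and 0.778 at 0.05 per side. For 80%, 24 completers (0.821) or 19 (0.809) are needed. Conversely, if one laser is truly better by 0.5, the single one-sided test of that laser passes with probability 0.9999, so passing says nothing about the upper side.

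**The case against.** The strongest reply is that the plan already has a valid route: Power and Sample Size states a non-inferiority goal, a margin and a one-sided alpha. That is right. A reader might infer that the plan has no margin at all; it does not bear that reading. The fault is confined to the satisfaction row's first step and to the offer of equivalence from one test.

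Four other stronger readings should be set aside.

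- **That the check inflates the comparison with placebo.** It does not, because the worse side is tested.
- **That "Assuming that the two methods are equivalent, we want to determine if the effect of either side would be better than a placebo effect" turns the check's result into an equivalence claim.** The phrase stands in the sample-size section and introduces a power table. It reads as a planning assumption, and nowhere does the plan say that the check will be reported as equivalence.
- **That the equivalence row lacks an outcome and a time point.** It may be a sub-row of VAS pain whose cells were lost in extraction. What survives either reading is that one one-sided test cannot show equivalence and that the row states no margin.
- **That 18 pairs always leave more than 20 points open.** With no discordant pairs, which is possible when one person rates both sides, the interval is about ±18 points.

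The plan also does not say what follows a significant difference, so the blocking effect in step 5 depends on a strict reading.

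**Conclusion.** Two statements in the analysis table are wrong as written and should be fixed.

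First, a non-significant difference in satisfaction cannot verify that the lasers are alike. The minimum-gap result (4/18 to 6/18) needs only N = 18 and alpha 0.05. The 63% to 86% pass rate rests also on the assumed rates and correlations. The harm is limited to an unsupported similarity statement and, on a strict reading, a blocked comparison with placebo.

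Second, the single one-sided t test supports non-inferiority only. The 0.80388 does not carry over to equivalence, for which 18 completers give 61% or 78% power under the plan's own SD and a true difference of zero. The sample size stands for non-inferiority.

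There is a separate conflict: Purpose & Objectives has "Primary Endpoint: Improvement in acne scarring measured by photographic review", while Power and Sample Size has "Sample size estimation is based on the primary aim of patient-reported scar improvement". That conflict, and Hypothesis 1 being worded as an absence of significant difference, are for the sponsor to reconcile. This point does not settle them.

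**What to change.** 1. **Satisfaction row.** Delete the preliminary check. Report the paired difference in proportions satisfied with its 95% CI, and do not report non-significance as similarity. Test the lower side against one reference rate fixed in advance, whatever the between-laser result. State that the 0.80 in the detectable-difference table is for one pre-named side, and that the lower-of-two exact test has about 34% to 64% power over the ten scenarios if the lasers are equal (ρ 0 to 0.4 assumed). If each side is tested separately and a win on either counts, add a multiplicity rule.
2. **Equivalence row.** Strike the words offering equivalence, or define it as two one-sided tests within ±0.5 and state the 61% or 78% power.
3. **Tie the test to its outcome.** The sponsor should first confirm which outcome the equivalence row belongs to, so that a planned pain analysis is not overwritten. Separately, write out the powered rule for the patient satisfaction score: non-inferiority is concluded if the lower limit of the two-sided 95% CI for the paired difference, new minus old laser, is above −0.5. This requires the sponsor to confirm that this trial's survey is scored 0 to 3 and which laser is the new one. If the scale differs, restate the margin, SD and sample size on that scale.

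**Cost.** SAP wording, with the same data and no extra patients if non-inferiority is the aim and the 0 to 3 scale is confirmed. The downside is a weaker permitted conclusion on similarity and a lower stated power for the lower-side test. Keeping equivalence at 80% power would need 24 or 19 completers: 24/0.9 = 26.7, so 27 enrolled, or 19/0.9 = 21.1, so 22 enrolled, against the 20 planned.
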